6.4 Level of Significance, Multiple Comparisons and Multiplicity

The primary objective of this study is to assess safety and tolerability of AG019. The study is descriptive in nature and is not designed to provide analytical results regarding efficacy.

6.5 Adjustment for Covariates

Not applicable as the output will contain no statistical analyses. Summary tables will show changes from baseline.

6.6 Handling of Dropouts and Missing Data

The data will be analysed as is except for missing dates for concomitant medication and adverse event, see those sections.

6.7 Multicentre Studies

Since this is only a small study primarily focused on safety no site or country effect will be studied.

6.8 Examination of Subgroups

No examination of subgroups is planned.

6.9 Interim Analysis

Preliminary results (interim analysis 1) for the open-label part of the study and a second interim analysis (described in the Interim Analysis Plan [IAP]) has been performed previously.

The primary analysis will be performed when all patients have passed the Day 180 visit. This interim analysis will contain the same TFLs that will be produced for the final output, if possible.

All decisions on data for blinded subjects will be taken before breaking the blind for the third interim analysis. Since this is a study of descriptive nature, with no statistical tests, the influence of the interim analyses should be considered negligible.

6.10 Data Monitoring

A Data Safety Monitoring Board (DSMB) has reviewed the eCRF-reported safety related data for all enrolled patients at predefined time points.

7 LIST OF OUTPUT

7.1 Tables to be Produced for the Clinical Study Report (Section 14 according to ICH E3)

(Table numbers refer to section numbers in ICH E3)

14.1 DEMOGRAPHIC DATA

(Baseline presentations will be based on the safety set if not otherwise stated below)

- Subject Disposition in Analysis Sets and Reason for Exclusion (all included subjects)
- Subject Discontinuation (all included subjects)
- Screening Failures including Reasons for Failure
- Demographics (age, sex and ethnicity)

- Background Characteristics (% of patients on insulin, HbA1c, insuline adjusted HbA1c, time from diagnosis to treatment start, EBC, CMV, HIV, HBV, HCV, GAD65 antibodies, IA-2 antibodies, ZnT8 antibodies and insulin antibodies)
- Weight, BMI and use of tobacco, alcohol and illicit drugs
- Baseline insulin use (dose in IU/kg and time from insulin start to treatment start)

14.2 EFFICACY DATA

Pharmacodynamic Assessments:

Summary statistics for absolute values and change from baseline for (PD Analysis Set):

- HbA1c
- Insuline dose adjusted HbA1c

Summary statistics for insulin use per kg body weight per visit (PD Analysis Set)

Pharmacodynamic Assessments - Figures:

- Average HbA1c
- Individual HbA1c values (spaghetti plots)
- Average insulin dose adjusted HbA1c
- Individual insulin dose adjusted HbA1c (spaghetti plots)

14.3 SAFETY DATA

(Safety presentations will be based on the safety set unless otherwise stated below)

- 14.3.1.x Summary of All Adverse Events for single dose AG019 patients
- 14.3.1.x Summary of All Adverse Events for repeat dose AG019 patients
- 14.3.1.x Summary of All Adverse Events for combination cohort patients
- 14.3.1.x All Adverse Events by System Organ Class and Preferred Term
- 14.3.1.x Treatment-Emergent Adverse Events by System Organ Class and Preferred Term
- 14.3.1.x Treatment-Emergent Adverse Events by System Organ Class and Preferred Term during AG019 treatment period
- 14.3.1.x Treatment-Emergent Adverse Events by Severity, System Organ Class and Preferred Term
- 14.3.1.x Treatment-Emergent Adverse Events by Severity, System Organ Class and Preferred Term during AG019 treatment period
- 14.3.1.x Treatment-Emergent Adverse Events by Relationship to AG019, System Organ Class and Preferred Term
- 14.3.1.x Treatment-Emergent Adverse Events by Relationship to AG019, System Organ Class and Preferred Term during AG019 treatment period

14.3.1.x Treatment-Emergent Serious Adverse Events by System Organ Class and Preferred Term

14.3.1.x Treatment-Emergent Adverse Events Leading to Premature AG019 Treatment Discontinuation by System Organ Class and Preferred Term

14.3.4.x Laboratory Measurements:
Summary Statistics by Visit with Difference from Baseline (Hematology & INR, Clinical Chemistry, Liver Function & CRP and HbA1c)
Shift Tables (Hematology & INR, Clinical Chemistry, Liver Function & CRP)
Figures of mean and median CRP, AST and Lymphocytes over time
Number of patients with positive/negative serology at baseline and positive/negative for PCR per visit
Summary of CGM Recording Time

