 the baseline visit. The CGM device will be placed, so the patient will know how to do this at
 home. The placement of the CGM, as well as the first CGM reading, will be done prior to
 administration of the first dose of study drug(s). The Sponsor will supply the CGM devices.
- **Tuberculosis test:** As part of the eligibility verification, all patients will undergo a test to determine whether the patient shows signs of active or latent tuberculosis. The decision on the type of test to be used is left to the discretion of the investigator, and could include e.g. TST, TSPOT, QuantiFeron or other appropriate tests.
- Concomitant medications: At every visit, the investigator will obtain information about concomitant medications the patient is taking (including dose, frequency, route of administration, start and stop dates)

6.2.Safety Assessments

Safety will be assessed by collecting and recording Adverse Events (AEs) and laboratory assessments and the presence of *L. lactis* sAGX0407 in whole blood.

The study will utilize local laboratories for safety assessments. The clinical laboratory will indicate laboratory values out of normal ranges. The Investigator must assess all abnormal clinical laboratory results for clinical significance in a timely fashion. A notation of 'clinically significant' (CS) or 'non-clinically significant' (NCS) with initials and date will be documented on the respective laboratory report next to any abnormal value. An abnormal clinical laboratory value will be considered and documented as an AE, if in the opinion of the Investigator, it is clinically significant. The Investigator will follow proper adverse event reporting procedures.

For details on the data to be collected for adverse events, please refer to Section 8.

XXX

6.3.Laboratory Assessments

6.3.1General considerations

Throughout the study, blood samples will be collected at regular intervals, as described in the Visit schedule

XXX

Confidentiality Statement

XXX

6.3.2Local lab assessments

Parameters to be analysed will include:

- Hematology: complete blood count: Red Blood Cell (RBC) count, haemoglobin, haematocrit, mean corpuscular volume (MCV), mean corpuscular haemoglobin (MCH), mean corpuscular haemoglobin concentration (MCHC), RBC distribution width (RDW), white blood cell (WBC) count, differential count, platelet count
- Serum Chemistry: blood glucose, sodium, potassium, chloride, calcium, CO₂/bicarbonate

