8.5. Adverse Event Follow-up Period

All patients with AEs will be followed until the event resolves, stabilizes, becomes chronic, the patient completes the study or the patient is lost to follow-up.

8.6.Serious Adverse Event Definition

In addition to classifying the AE as mild, moderate, severe, life-threatening or fatal, the Investigator should determine whether or not an AE is an SAE. The Investigator shall make an accurate and adequate report on any SAE to the Sponsor or its designee and to any IRB/IEC that has reviewed and is continuing to review the study regarding any SAEs (see Sections 8.7 and 8.9).

An SAE is defined as any AE occurring at any dose regardless of relationship to IMP that results in any of the following outcomes:

- results in death,
- is life-threatening, NOTE: The term "life-threatening" in the definition of "serious" refers to an event in which the patient was at risk of death at the time of the event; it does not refer to an event which hypothetically might have caused death if it were more severe.
- requires inpatient hospitalization or prolongation of existing hospitalization,
- results in persistent or significant disability/incapacity, or
- is a congenital anomaly/birth defect.

Medical and scientific judgement should be exercised in deciding whether expedited reporting is appropriate in other situations, such as important medical events that may not be immediately lifethreatening or result in death or hospitalization but may jeopardize the patient or may require intervention to prevent one of the other outcomes listed in the definition above. These should also usually be considered serious. Examples of such events are intensive treatment in an emergency room or at home for allergic bronchospasm; blood dyscrasias or convulsions that do not result in hospitalization; or development of drug dependency or drug abuse.

The following situations will be considered important medical events and must be reported as SAEs:

Confidentiality Statement

- 1. Grade 4 or higher lymphopenia for 7 or more days occurring in the first 30 days after the start of the teplizumab infusion.
- 2. Grade 3 or higher lymphopenia occurring anytime later than the first 30 days after the start of the teplizumab infusion.

Complications that occur during hospitalization are AEs. If a complication prolongs hospitalization, the event causing the prolongation is an SAE. Planned hospitalizations are not considered SAEs.

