10.7. Safety Analysis

Safety will be assessed based on TEAEs, physical examination findings, vital sign measurements and clinical laboratory tests.

Adverse events will be coded to a Medical Dictionary for Regulatory Activities (MedDRA) preferred term and system organ classification. The occurrence of treatment emergent AEs will be summarized by treatment frequency received using preferred terms, system organ classifications and severity. If a patient experiences multiple events that map to a single preferred term, the greatest severity and/or strongest investigator assessment of relation to study drug will be assigned to the preferred term for the appropriate summaries. Separate summaries of treatment emergent SAEs and treatment emergent AEs that are related to either IMP will be generated. Summaries may be repeated according to study phase. All AEs will be listed for individual patients showing both verbatim and preferred terms.

Descriptive summaries of vital signs and quantitative clinical laboratory changes will be presented by treatment received and study visit. The number and percentage of patients experiencing laboratory abnormalities and clinically relevant laboratory abnormalities will be summarized by treatment received. Cross tabulations of baseline abnormality vs. worst post treatment abnormality for selected laboratory assessments will presented by treatment received.

Abnormal physical examination findings will be presented by treatment received. The number and percentage of patients experiencing each abnormal physical examination finding will be included.

Prior and concomitant medications will be coded using the World Health Organization (WHO) dictionary. These data will be listed.

The number and percentage of patients with presence of sAGX0407 bacteria will be summarized by treatment group.

10.8.Interim Analysis

Interim analyses will be performed according to the below schedule:

After the last Day 180 follow-up visit of the last patient enrolled into the Phase 1b portion of
the study, a preliminary analysis of the data collected up to 6 months will be performed for
these patients.

Confidentiality Statement

- Once all patients enrolled in Combination Cohort 1, as well as the 2 patients enrolled into the
 open label portion of Combination Cohort 2, have completed the Day 180 follow-up visit,
 unblinding will be done and an interim analysis will be performed.

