6.3.9 Other Safety Assessments

Vital Signs

For repeat dose patients, weight, sitting blood pressure, heart rate, respiratory rate and body temperature will be measured at Visit 1, 2, 5, 8, 13-19. Height is measured at Visit 1. For single dose patients vital signs will be measured at screening, treatment and post treatment.

For all vital signs parameters summary statistics will be produced for observed values. In addition, the difference from baseline to each visit at which they were assessed will be derived and presented.

Shift tables showing the number of subjects who changed from normal, abnormal not clinical significant or abnormal clinical significant at baseline to normal, abnormal not clinical significant or abnormal clinical significant at each post-baseline time of assessment will be presented.

All vital signs will be listed.

Clinical Laboratory Measurements

From screening to the last visit lab parameters will be collected, see CSP Appendix A for details.

Parameters to be analysed will include:

- Hematology: complete blood count: Red Blood Cell (RBC) count, haemoglobin, haematocrit, mean corpuscular volume (MCV), mean corpuscular haemoglobin (MCH), mean corpuscular haemoglobin concentration (MCHC), RBC distribution width (RDW), white blood cell (WBC) count, differential count, platelet count
- Serum Chemistry: blood glucose, sodium, potassium, chloride, calcium, CO₂/bicarbonate
- Liver function tests: alkaline phosphatase (ALP), Aspartate Aminotransferase (AST), Alanine Aminotransferase (ALT), lactate dehydrogenase (LDH), total protein, albumin, total bilirubin
- Pregnancy tests for women of childbearing potential: serum (at screening), urine (at other visits)
- Coagulation tests: international normalized ratio (INR)
- Inflammatory: C-reactive protein (CRP)

Following additional blood parameters will be analysed at screening, and if no concerns are identified, these parameters will not require analysis at follow-up visits:

- Kidney function tests: uric acid, urea/blood urea nitrogen (BUN), creatinine, estimated glomerular filtration rate (eGFR)
- Cardiovascular tests: total cholesterol, triglycerides, high density lipoproteins (HDL), low density lipoproteins (LDL), very low density lipoproteins (VLDL - optional)
- Thyroid stimulating hormone (TSH)

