In addition to the above lab assessments to be analysed by the site's local lab, EBV/CMV/HCV/HBV/HIV monitoring assessments will be done. These measurements were performed at screening for all patients and at Visit 13-16, Visit 19 for repeat dose patients. Potential reactivation will be assessed at regular intervals by polymerase chain reaction (PCR) for viral load.

For hematology, clinical chemistry, liver function, coagulation parameters and CRP summary statistics will be produced for observed values. In addition, the difference from baseline to each visit at which they were assessed will be derived and presented.

Shift tables showing the number of subjects who changed from normal, abnormal not clinical significant or abnormal clinical significant at baseline to normal, abnormal not clinical significant or abnormal clinical significant at each post-baseline time of assessment will be presented.

Figures showing mean and median values over time per cohort will be shown for CRP, AST and lymphocytes.

Number of patients with positive/negative serology at baseline and positive/negative for PCR per visit will be tabulated.

All laboratory parameters will be listed. Abnormal values will be flagged in listings.

In addition, all study patients (except for the single dose patients) will receive a XXX continuous glucose monitor (CGM) device for the entire duration of their study participation. The data generated by the device will be downloaded at every site visit. The devices will store data for up to 30 days. The device measures glucose every 5 minutes, thus every measurement will be said to have a duration of 5 minutes when the calculation of total duration is performed. The first measurement is said to measure the glucose value 5 minutes before the actual measurement. For the CGM data collected at each visit:

- The total CGM recording time,
- Time in range (the time greater than or equal to 71 mg/dl and less than or equal to 179 mg/dl),
- Time above range (the time above 179 mg/dl),
- Time in the low range (the time below 71 mg/dl),
- Time in the very low range (the time below 50 mg/dl) and
- Time with missing values

will be summarized in hours/minutes and percentages of the total CGM recording time, per cohort.

Physical Examination

The physical examination included visual inspection of skin, examination of eyes, ears and throat, auscultation of heart, lungs and abdomen, and percussion/palpation of abdomen. The results will be recorded as

- Normal,

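### The laboratory shift tables carry no direction, so low and high values of the same significance class share a cell and a high-to-low reversal is hidden

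*SAP*

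**What the plan says.** SAP 7.1, in the block for laboratory measurements under 14.3, plans "Shift Tables (Hematology & INR, Clinical Chemistry, Liver Function & CRP"). The categories come from the laboratory part of SAP 6.3.9: "Shift tables showing the number of subjects who changed from normal, abnormal not clinical significant or abnormal clinical significant at baseline", and the same three at each later assessment. Haematology there includes "white blood cell (WBC) count, differential count, platelet count", so lymphocytes are covered through the differential count.

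Protocol 6.2 explains where the categories come from. First, "The clinical laboratory will indicate laboratory values out of normal ranges". Then the investigator classifies each abnormal value: "A notation of 'clinically significant' (CS) or 'non-clinically significant' (NCS) with initials and date will be documented on the respective laboratory report". Only a value judged clinically significant becomes an adverse event.

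Protocol 10.7 describes its own version of the table: "Cross tabulations of baseline abnormality vs. worst post treatment abnormality for selected laboratory assessments will presented by treatment received". It names no direction either.

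Protocol 8.6 makes certain low lymphocyte counts reportable as SAEs whatever the investigator's view of significance. One is Grade 4 or above lasting at least 7 days within 30 days of starting teplizumab. The other is "Grade 3 or higher lymphopenia occurring anytime later than the first 30 days after the start of the teplizumab infusion".

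**The concern.** A laboratory shift table should show how many patients left the normal range, and which way. Many of the listed parameters can go out of range in either direction, and the two directions mean different things. Lymphocytes are the clearest case. The protocol sets an entry floor of 1,000/µL and treats specified lymphopenia as an SAE, so the fall is the movement of interest after teplizumab. A table that puts falls and rises in the same cell cannot give that count.

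The study is descriptive and has no tests (SAP 6.4 and 6.5). Its tables are the analysis, and laboratory variables are secondary safety endpoints (SAP 3.2). If a table cannot separate low from high, the patient counts for those endpoints are incomplete.

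**Working it through.** The plan states no figure to reproduce. The check is an enumeration, followed by a reading of what the other outputs recover.

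**Inputs.** Three SAP categories (SAP 6.3.9). Five directional states that a two-sided parameter can take: low CS, low NCS, normal, high NCS, high CS.

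**Step 1: how many moves share a cell.** Directional moves: 5 × 5 = 25. SAP cells: 3 × 3 = 9.

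| SAP cell (baseline → visit) | Directional moves pooled | Of these, high/low reversals |
|---|---|---|
| Normal → Normal | 1 | 0 |
| Normal → NCS; Normal → CS | 2 each | 0 |
| NCS → Normal; CS → Normal | 2 each | 0 |
| NCS → NCS; CS → CS (diagonal) | 4 each | 2 each |
| NCS → CS; CS → NCS | 4 each | 2 each |

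Moves: 1 + 2×2 + 2×2 + 2×4 + 2×4 = 25. Reversals: 2×2 + 2×2 = 8.

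- 4 of the 8 reversals lie on the diagonal and read as no shift.
- The other 4 lie off the diagonal but show only a change between NCS and CS.
- From a normal baseline, each abnormal cell pools one fall and one rise.

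**Step 2: what a count can hide.** Each combination cohort has 2 open-label patients plus 10 randomised 4:1, so 2 + 10 × 4/5 = 10 active patients. Suppose, as an assumption, that 8 of the 10 move from normal to abnormal NCS in lymphocytes. The cell shows 8. The number who went low could be anything from 0 to 8, and the table would look the same.

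**Step 3: reach.** SAP 6.3.9 lists 10 haematology, 6 chemistry and 7 liver entries plus INR and CRP: 10 + 6 + 7 + 1 + 1 = 25. Assume that all haematology entries except RDW, and all chemistry entries, can be abnormal both ways. That is general laboratory knowledge, not document text. Then 9 + 6 = 15 are two-sided, or 14 without glucose. This says how many parameters are affected, not how far any conclusion would change.

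**Step 4: what the other outputs recover.**

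- *By-visit summaries* (SAP 6.3.2 and 6.3.9) give mean, median, minimum and maximum of values and of changes. They show that movement occurred in a direction, but not how many patients crossed a limit. The safety laboratories are local.
- *Figures* of mean and median lymphocytes show direction for the cohort only.
- *Listings* show every value with abnormal ones flagged. The flag is not said to be high or low, and the reader must do the counting.
- *Adverse event tables* can show direction through the preferred term, for values judged CS.
- *SAE reporting* adds lymphopenia that meets the Protocol 8.6 thresholds.

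An NCS value below those thresholds reaches no adverse event table. For haematology and electrolytes, no table in SAP 7.1 counts such patients by direction.

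**Step 5: after the change.** With direction kept, all 8 reversals fall off the diagonal, against 4 of 8 now. The full layout has up to 25 cells instead of 9.

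**The case against.** The strongest reply is that direction is lost from one display, not from the report. A clinically significant fall in lymphocytes is an adverse event, tabulated by preferred term and severity. Prolonged or late severe lymphopenia is an SAE. Lymphocytes are one of only three parameters given their own figures. Minimum and maximum changes reveal opposite movements. AG019 repeat-dose cohorts have at most 6 patients and combination cohorts 12, so the listings can be read patient by patient. Protocol 10.7 does not ask for direction, so the SAP breaks no commitment by omitting it.

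Most of this stands. It narrows the gap to patient counts by direction, mainly for values judged NCS. It does not close it, because those patients can be counted only by hand from the listings.

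A reader might infer more than the documents support:

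- *Every high-to-low change reads as no shift.* That holds only when the significance class is unchanged.
- *The shift tables are the only categorical laboratory summaries.* SAP 6.3.9 also plans PCR and serology counts, CGM time in ranges and a summary of hypoglycaemic events.
- *A fall to low glucose would be missed.* The CGM ranges and the hypoglycaemia table are directional and serve that purpose better.
- *The categories ignore the reference range.* Under Protocol 6.2 the laboratory marks out-of-range values. Only the CS/NCS split is judgement.

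**Conclusion.** The point holds for the laboratory shift tables. As written, they pool low and high values of the same significance class. Of the 8 high/low reversals, they show 4 as no shift and 4 as a change of significance only. The practical loss is moderate: patient counts of low versus high haematology and electrolyte values, in particular those judged NCS. It does not follow that important lymphopenia would go unreported, since the adverse event and SAE rules still apply.

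The conclusion rests on the SAP text. The table shells are not in the documents, so a directional layout there cannot be excluded, but nothing in SAP 6.3.9 or 7.1 provides for one. It also assumes that the parameters named in the fix have two-sided ranges.

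The vital-sign shift tables use the same three categories, and a reader might extend the point to them. That is not pursued here. The documents state no vital-sign limits, so direction there would need new limits for adults and for ages 12-17.

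**What to change.** In the laboratory part of SAP 6.3.9 and in the 14.3.4 entries of SAP 7.1, define the shift categories for two-sided parameters as Low / Normal / High against the local laboratory range, at baseline and at each later visit. Show the investigator's CS/NCS flag as a sub-count within Low and within High. Apply this at least to lymphocytes and the other differential counts, platelets, haemoglobin and electrolytes. One-sided parameters can keep the present layout.

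The cost is larger tables: 9 main cells as now, up to 25 with the sub-counts. The local range or a high/low flag must also be in the database. Protocol 6.2 has the laboratory mark out-of-range values, but the documents do not say whether the range or the direction of the mark is captured. If it is, the change is SAP wording and table shells. If not, the ranges must be obtained from the local laboratories first. Sample size and error rates are unaffected, since no tests are planned.
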